7.2. Randomisation, blinding and treatment allocation

This is a phase 3 non-blinded non-placebo controlled pragmatic trial. Randomization will be stratified according to the following 3 risk groups: Acute myeloid leukemia, graft-versus host disease and other.

Randomization and concealed allocation will be performed and guaranteed via randomization using blocks of different length and with the use of a randomization module

in the eCRF (Alea). Subjects will be randomized to a 1:1 allocation into 2 treatment group: monotherapy versus combination therapy.

7.3. Study procedures

The study procedures involve a screening visit and follow-up up to week 24 for overall mortality. Taking the pragmatic design into account, this means that a formal hospital visit is not required for the primary endpoint evaluation after the patient is discharge from the hospital. However, investigators and patients will be encouraged to facilitate the collection of additional data as described in appendix 2 as much as possible to allow for the evaluation of several secondary endpoints in a large study population. Because these data are part of routine medical registration procedures (e.g. use of blood products, hospital days, ICU days, use of medication, blood test results) this will not obstruct the analysis of these secondary endpoints.

All patients will be receiving triazole therapy as prescribed by their treating physician at the time of screening for study participation. Monitoring for treatment related adverse events will be performed as per standard of care during triazole antifungal therapy and typically includes liver enzyme monitoring at least once a week during the first weeks of therapy. Given the overall very good safety profile of anidulafungin and the fact that it can only be administered intravenously at the hospital, no additional safety evaluations are needed.

7.4. Withdrawal of individual subjects

Subjects can leave the study at any time for any reason if they wish to do so without any consequences. The investigator can decide to withdraw a subject from the study for urgent medical reasons. Patients leaving the study will receive treatment as deemed appropriate by their treating physician

After randomization, the following patients will leave the interventional part of the study, but clinical data will continue to be collected:

- 1. Patients in whom none of the mycological criteria as described in appendix 1 have become positive within 8 days after randomization. This may be as soon as 48hrs after (e.g. if serum and BAL galactomannan testing and fungal culture result is final 48hrs after randomization).
- 2. Patients in the Netherlands in whom the resistance tests were unsuccessful (asper-gillus culture remained negative and aspergillus PCR demonstrated the presence of A. fumigatus but the resistance PCR is unsuccessful) will receive further treatment according to the choice of the treating physician because guidelines recommend to treat these patients with an azole in combination with a second antifungal drug. If the patient was randomized to the anidulafungin arm, the option will be given to

continue anidulafungin for up to 4 weeks, but these patients will be excluded from the MITT population (see 7.1.4) The 24-week outcome of these patients will be registered. In Belgium, currently no guidelines are in place recommending combination therapy for this patient group. Therefore, this does not apply to Belgian patients. Please note that patients in whom the Aspergenius PCR documents the presence of an aspergillus spp. other than fumigatus will remain in the study and will be included in the MITT population. This specific conclusion will be drawn when the aspergillus spp. PCR is positive with a CT value of 35 or lower but the aspergillus fumigatus PCR is negative as this demonstrates the presence of a non-fumigatus aspergillus infection.

7.5. Replacement of individual subjects after withdrawal

As anidulafungin has limited side-effects, a low percentage of withdrawal can be expected, and patients withdrawn from the study will not be replaced.

7.6. Follow-up of subjects withdrawn from treatment

Patients withdrawn from the study will be followed for overall mortality only

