5. TREATMENT OF SUBJECTS

5.1. Investigational product/treatment

Anidulafungin

Detailed information on anidulafungin, the investigational product used in this study can be found in the SPC. A short summary is given here. The information currently available on combination therapy with a triazole and an echinocandin for the treatment of IA is described below (6.2).

Mechanism of action

Anidulafungin is a semi-synthetic echinocandin, a lipopeptide synthesised from a fermentation product of Aspergillus nidulans. Anidulafungin selectively inhibits 1,3-8-D glucan synthase, an enzyme present in fungal, but not mammalian cells. This results in inhibition of the formation of 1,3-beta-D-glucan, an essential component of the fungal cell wall. Anidulafungin has shown fungicidal activity against Candida species and activity against regions of active cell growth of the hyphae of Aspergillus fumigatus.

Chemical Name

Anidulafungin has the chemical name 1-[(4R,5R)-4,5- Dihydroxy-N2- [[4"-(pentyloxy) [1,1':4',1"-terphenyl]- 4- yl]carbonyl]- Lornithine]echinocandin B.

Name of medicinal product

ECALTA 100 mg powder for concentrate for solution for infusion

Method of administration

For intravenous use only.

ECALTA should be reconstituted with water for injections to a concentration of 3.33 mg/mL and subsequently diluted to a concentration of 0.77 mg/mL.

Dosage & duration

Adult patients receive a loading dose on day-1 of 200mg IV, followed by 100 mg daily thereafter.

Anidulafungin will be given for at least 7 days but no longer than 28 days. Please note that this refers to the MITT primary endpoint population. In patients in which triazole resistance is demonstrated or in which the results of the resistance test are inconclusive, the treatment duration of combination therapy can be much longer. These patients are not included in the MITT primary endpoint population.

Intervention

Treatment with a triazole (voriconazole or isavuconazole or posaconazole) + anidulafungin IV. The triazole is administered for at least 6 weeks while anidulafungin is given for at least 7 and a maximum of 28 days.

Comparator

Treatment with a triazole (voriconazole or isavuconazole or posaconazole) for at least 6 weeks.

In both groups, the route of administration is according to the choice of the treating physician as well as the decision to perform or not perform therapeutic drug monitoring of the triazole drug.

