8.3. Serious Adverse Events

8.3.1. Reporting of serious adverse events

Serious Adverse Events (SAEs) will be reported from the first administration of treatment according to protocol until day 14 days after the last dose of the IMP or until the start of subsequent systemic therapy for the disease under study, if earlier.

Serious adverse events (including death) occurring after day 42 days should also be reported if considered at least possibly related to the investigational medicinal product by the investigator.

SAEs must be reported to HOVON Data Center within 3 days after the event was known to the investigator, using the SAE report form provided. This initial report should contain a minimum amount of information regarding the event, associated treatment and patient identification, as described in the detail in the instructions for the SAE report form. Complete detailed information should be provided in a follow-up report within a further 7 business days, if necessary.

The following events do not require to be reported as a serious adverse event:

- Relapse/Progression of the disease under study. However, death or complications as a result of disease progression should be reported as serious adverse events if occurring within 14 days after last dose of study drug.
- "Hospitalization for protocol therapy administration. Hospitalization or prolonged hospitalization for a complication of therapy administration will be reported as a serious adverse event.
- "Hospitalization for diagnostic investigations (e.g., scans, endoscopy, sampling for laboratory tests, bone marrow sampling) that are not related to an adverse event. Hospitalization or prolonged hospitalization for a complication of such procedures remains a reportable serious adverse event.
- " Prolonged hospitalization for technical, practical, or social reasons, in absence of an adverse event.
- Hospitalization for a procedure that was planned prior to study participation (i.e. prior to registration or randomization). This should be recorded in the source documents. Prolonged hospitalization for a complication of such procedures remains a reportable serious adverse event.

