12. ADMINISTRATIVE ASPECTS, MONITORING AND PUBLICATION

12.1. Handling and storage of data and documents

Data will be handled confidential and if possible, anonymously. Where it is necessary to be able to trace data to an individual subject, a subject identification code list will be used to link the data to the subject. The code will not be based on the patient initials and birthdate. The key to the code will be safeguarded by the investigator. as the data and human material will be kept for a longer period of time. The handling of personal data will comply with the Belgian and Dutch Personal Data Protection Act (in Dutch: De Wet Bescherming Persoonsgegevens, Wbp).

Case record form (CRF)

All data of patients, including results from standard procedures during treatment, collected during the study will be recorded in Case Record Forms. The CRF must be completed fully and legibly. Corrections of possibly erroneous entries must be carried out in such a manner that the initial entry is not rendered illegible. Corrections should be written alongside or above the pertinent place with the date and initials. Correction fluid must not be used.

The investigators are responsible for the quality of the data recorded in the Case Record Forms (CRF). Where the investigators have not been responsible for completing the CRF, an additional signature from the co-investigator overseeing the data entry of the study must be obtained.

In the event that the investigators need to deviate from the protocol, the nature of and reasons for protocol deviation must be recorded in the hospital patient record and in the CRF. In nearly all cases it is desirable that the patient continues the study to allow the most informative intention-to-treat analysis; This does not mean that the treatment to which the patient was randomized needs to be continued. As illustrated by the flow diagram of the study (figure 1) there can be good reasons to change antifungal therapy after randomization. However, also for patients that go off study for the 3 reasons mentioned in figure 1, a limited number of data will be collected in the CRF (e.g. antifungal therapy, survival)

Privacy rules

Patients will be identified in the CRF by their identification code. The investigators will keep a patient identification log, including sufficient information to link the hospital record and CRFs.

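### Section 7.6 (mortality only) contradicts 7.4, 12.1 and the SAE window in 8.3.1/8.7, and the subsequent-therapy cut-off can close SAE reporting while anidulafungin is still being given

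*Protocol*

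**What the plan says.** Five places in the protocol govern what is collected once a patient stops following the randomised plan.

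- **7.6** is one unqualified sentence: "Patients withdrawn from the study will be followed for overall mortality only". Its heading speaks of withdrawal from treatment, its body of withdrawal from the study.
- **7.4** names two groups who, after randomisation, "will leave the interventional part of the study, but clinical data will continue to be collected". They are patients with no positive mycological criterion within 8 days, and Dutch patients whose resistance tests were unsuccessful. Those in the second group who were randomised to anidulafungin may "continue anidulafungin for up to 4 weeks, but these patients will be excluded from the MITT population". Their 24-week outcome is registered.
- **12.1** says a limited data set is kept in the CRF for patients who go off study for the three reasons in figure 1, with antifungal therapy and survival as examples.
- **8.3.1 and 8.7** set the SAE window from first protocol treatment to 14 days after the last dose of the investigational product, "or until the start of subsequent systemic therapy for the disease under study, if earlier". Section 8.3.1 adds that SAEs after day 42 are reported if at least possibly related to the product.
- **5.1** says that in resistant or inconclusive cases, outside the primary MITT population, "the treatment duration of combination therapy can be much longer".

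**The concern.** A site has no rule telling it which of these sections prevails. If it follows 7.6, it records whether the patient died and nothing else, although the 14-day post-dose window in 8.3.1 may still be open. If it follows 8.3.1, reporting can still close early because another systemic antifungal was started, even though anidulafungin continues.

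This trial has little else to fall back on for safety. Non-serious events are not reported (8.2.1), no DSMB is planned (8.8), and no safety evaluations beyond standard care are foreseen (7.3). SAE reports feed the SUSAR assessment (8.3.4, 8.4) and the annual safety report (8.6). Deaths would still be known from survival status. What would be lost is the non-fatal SAE and the causality assessment that goes with an SAE report. The loss would fall selectively on patients who have left the study after exposure to the investigational product.

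**Working it through.** No stated figure is under test here. The check sets the sections side by side and works out the SAE window.

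**Step 1. Do 7.6 and 7.4 cover any of the same patients?** Inclusion criterion 7 (section 4.2) allows certain AML, ALL and GVHD patients to enter before mycology is known. It says they are withdrawn from the study if the tests are negative, which is the term 7.6 uses. Section 7.1.3 likewise says such patients leave the study. They are also the first group in 7.4, for whom clinical data collection continues. So at least this group falls under both rules.

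**Step 2. What does 8.3.1 require for them?** Window end = day of last dose + 14.

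- Last dose on day 7: 7 + 14 = day 21.
- Last dose on day 28: 28 + 14 = day 42.

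A mycology-negative patient in the combination arm who stops anidulafungin on day 7 is owed SAE reporting to day 21 under 8.3.1 and 8.7. Under a literal 7.6, only death is recorded from the day of withdrawal.

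**Step 3. Can the window close during dosing, leaving 7.6 aside?** Take a Dutch patient in the combination arm. The days are assumed for illustration: the resistance test fails on day 6, the physician starts a further systemic antifungal that day, and anidulafungin continues to day 28, as 7.4 permits.

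- The if-earlier limb of 8.3.1, repeated in 8.7, can be read as closing reporting on day 6.
- Dosing that remains after closure: 28 − 6 = 22 days.
- Without that limb the window would run to 28 + 14 = day 42.
- The possibly-related clause starts only after day 42, so it covers none of the interval from day 6 to day 42 (42 − 6 = 36 days), even for a related event.

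**Step 4. Duration.** Four weeks in 7.4 is 4 × 7 = 28 days, the same as the 28-day maximum in 5.1 for the MITT population. The open-ended sentence in 5.1 gives no limit. The two sections differ for patients with inconclusive resistance results.

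**Step 5. Off-study groups.** Section 7.4 lists two, while 12.1 refers to three in figure 1. The figure could not be seen in the text reviewed, so the third reason cannot be confirmed.

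**The case against.** The strongest reply is that this is loose wording rather than a rule that stops safety reporting. Section 7.4 separates subjects who are withdrawn altogether from those who leave only the interventional part, and 7.6 may be meant for the former. Sections 8.3.1 and 8.7 tie SAE reporting to the last dose, not to study status, and no section says that reporting ends at withdrawal. The list in 12.1 is open and need not exclude SAEs. In Step 3, a combination-arm patient already receives an azole plus a second antifungal, so the added drug is an assumption. Calling an add-on subsequent therapy is an interpretation.

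Much of this stands. It rules out three stronger readings that a reader might infer:

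- **That every patient who leaves while on anidulafungin is followed for mortality only.** The Dutch failed-test group is expressly placed under continued clinical data collection in 7.4.
- **That the gap falls on the patients with the longest exposure.** Only 5.1 suggests this. It speaks of combination therapy without saying that the extra time is on study anidulafungin, and the limit in 7.4 equals the ordinary maximum.
- **That the number affected can be estimated.** The 35% of uninterpretable resistance tests (section 1) is not confined to the narrower Dutch group in 7.4. The share outside the mITT population of the earlier combination trial (6.2) mainly resembles the mycology-negative group, who are not offered continued anidulafungin. Neither counts patients still being dosed after leaving.

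The reply does not remove the overlap in Step 1, because inclusion criterion 7 uses the same term as 7.6 for a group that 7.4 keeps under data collection. Nor does it answer the if-earlier limb, which makes no allowance for continued anidulafungin.

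**Conclusion.** The point holds as an inconsistency with a safety consequence on a literal reading. Section 7.6 conflicts with 7.4, 12.1 and 8.3.1/8.7 for at least the mycology-negative patients, and SAE collection can then stop within the 14-day post-dose window. Independently, the subsequent-therapy cut-off can end SAE reporting during anidulafungin dosing in a Dutch patient with an unsuccessful resistance test, with no fallback for related events until after day 42.

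The size can be given only in days per patient: up to 14 days after the last dose in the first case, and 22 days of dosing plus the 14 days after it in the illustrated second case. The second figure rests on the assumed day 6 and on an added antifungal counting as subsequent therapy. The primary mortality analysis is not affected. The text should be corrected because SAEs are the main safety information this trial collects.

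**What to change.** - **7.6:** state that any patient who received at least one dose of anidulafungin stays under SAE reporting until 14 days after the actual last dose, whatever the reason for leaving, unless consent to data collection is withdrawn.
- **8.3.1 and 8.7:** state that the subsequent-therapy cut-off does not apply while anidulafungin is still being given.
- **7.4 and 12.1:** align both with the above, and give the same list of off-study groups in each.
- **5.1 and 7.4:** the sponsor must reconcile these on how long anidulafungin may continue in patients outside the MITT population. This review takes no position on the duration.

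The cost is protocol wording and a small additional SAE reporting load at sites that already record therapy and survival for these patients. No extra visits are needed.

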7.7. Premature termination of the study

One interim futility analysis will be performed at the time when the 6-week survival of 50% of the planned sample size of 474 evaluable patients (=237) has become available. If this interim analysis shows that the conditional power after further enrolment of the remaining study population of observing the anticipated 33% reduction in the incidence of the primary endpoint in favor of combination therapy is <10%, the study team (the PI's from Erasmus MC, UZ Leuven and Radboud UMC, the study statistician, a delegate from KCE and from ZONMW and a patient representative) will meet to decide upon further enrollment. This decision will not only take the conditional power into account but also the recruitment speed as well as the relative decrease in mortality observed with the intervention under study (e.g. it may still be useful to continue the study if a 50% rather than a 30% decrease in overall mortality is observed when the conditional power to demonstrate a 30% is <10% as a result of a lower than expected overall absolute mortality in the control arm).

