8.8. Data Safety Monitoring

No data safety monitoring board (DSMB) will be implemented because the investigational product has been very well tolerated in the phase II and III studies and a previous fase III trial did not show any increase in AE or SAE in the anidulafungin voriconazole combination arm compared with the voriconazole monotherapy arm.

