9.3. Multiplicity

There is only 1 primary endpoint and no interim analysis for efficacy will be performed. Therefore, the primary endpoint will be tested at the α =0.05 level (two-sided test).

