9.5. Sample size calculation

In the pivotal trial on voriconazole and anidulafungin combination therapy the mortality in the voriconazole control group was 28% 6 weeks after the start of therapy. This study only included patients with an underlying haematological disease. Furthermore, in a large pragmatic trial with fewer exclusion criteria and in which a small number of ICU patients will be included as well, we expect a somewhat higher mortality of 35%, We consider a 33% lower overall mortality with combination therapy (=from 35% to 23,33%) compared to monotherapy of clinical importance. This leads to a sample size of 237 evaluable patients per group (=included in the mITT population as defined above) to show superiority of combination therapy compared with monotherapy with an alfa of 0.05 and a power of 80%. Follow-up for the primary endpoint is 6 weeks after the start of antifungal therapy.

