9.6. Responsibility for data analysis

The coordinating investigator will be responsible for analyzing the study data.

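### Section 7.7 lets the principal investigators weigh the observed between-arm mortality effect at the futility meeting of an open-label trial with no DSMB, with no stated limit on access and an override example that is not realistic

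*Protocol*

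**What the plan says.** Section 7.7 places one futility analysis at the point where 6-week survival is known for 237 of the 474 planned evaluable patients. If conditional power is below 10%, a meeting decides on further enrolment. It consists of "the study team (the PI's from Erasmus MC, UZ Leuven and Radboud UMC, the study statistician, a delegate from KCE and from ZONMW", together with a patient representative. The decision is not tied to conditional power alone. It also takes in "recruitment speed as well as the relative decrease in mortality observed with the intervention under study". The one illustration given is that continuing may still be useful if a 50% reduction is seen while conditional power is below 10% because control mortality turned out low.

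Section 8.8 says "No data safety monitoring board (DSMB) will be implemented because the investigational product has been very well tolerated". That reason concerns tolerability and does not address the futility look. Section 9.6 says "The coordinating investigator will be responsible for analyzing the study data". Section 7.2 describes the trial as non-blinded and without placebo. Sections 9.3 and 9.8 confirm that there is no interim efficacy analysis. None of these sections restricts access to interim results by arm.

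**The concern.** The protocol itself fixes both who decides and what they look at, so this is not a detail left to an analysis plan. Under the rule, three principal investigators see how the arms compare half-way through an open-label trial and may then continue it.

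Section 7.1.3 defends the open design by the objectivity of the endpoint. That protects the ascertainment of death. It does not protect the steps that depend on judgement:

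- exclusion in the investigator's opinion (section 4.3, criterion 9);
- the length of anidulafungin treatment between day 7 and day 28 (sections 3 and 5.1, Appendix 2);
- added antifungals in control patients, a temptation that section 5.3 itself acknowledges;
- the grading of deaths as attributable to aspergillosis (section 7.1.2, secondary endpoint 1).

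Knowledge of the interim effect could shift any of these in the remaining patients and would weaken the credibility of the result.

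**Working it through.** **1. The plan's own sample size.** Inputs from sections 9.3 and 9.5: "the primary endpoint will be tested at the α =0.05 level (two-sided test"; "with an alfa of 0.05 and a power of 80" percent; "We consider a 33% lower overall mortality with combination therapy (=from 35% to 23,33" percent. The pooled two-proportion formula, with mean rate 0.29165, gives

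n = [1.96·√(2·0.29165·0.70835) + 0.8416·√(0.35·0.65 + 0.2333·0.7667)]² / 0.1167² = 236.9, rounded up to 237.

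This reproduces "This leads to a sample size of 237 evaluable patients per group". The interim is at information fraction 237/474 = 0.5, or about 118.5 per arm.

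**2. When the meeting is called.** The planned drift is 0.11667/√[(0.2275 + 0.1789)/237] = 0.11667/0.04141 = 2.82. With interim statistic Z and assumed drift θ for the remaining patients, conditional power (CP) for a significant final result is

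CP = Φ{(Z·√0.5 + 0.5·θ − 1.96)/√0.5}.

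CP = 10% requires Z·√0.5 + 0.5·θ = 1.96 − 1.2816·0.7071 = 1.054. Section 7.7 does not say which θ applies, so three conventions are shown. Under the planned effect the interim Z has mean 2.82·0.7071 = 1.99. One unit of Z is √(2·0.2917·0.7083/118.5) = 5.9 percentage points.

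| θ for the remaining patients | Meeting if Z below | Observed difference at that Z | Chance, no true effect | Chance, planned effect true |
|---|---|---|---|---|
| planned (2.82) | −0.50 | 3.0 points against combination | 31% | 0.6% |
| current trend (Z/√0.5) | 0.75 | 4.4 points in favour | 77% | 11% |
| none (0) | 1.49 | 8.8 points in favour | 93% | 31% |

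The meeting is therefore not a remote event if the combination does not work.

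**3. The override example, for a significant result.** With control mortality p and an observed 50% reduction, the mean rate is 0.75p and

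Z(p) = (p/2)/√[2·0.75p·(1 − 0.75p)/118.5].

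This gives Z = 3.06 at p = 35%, 2.16 at 20%, 1.46 at 10% and 1.01 at 5%.

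- Current trend: Z(p) = 0.745 at p = 2.75%, so control mortality must be below about 2.8%. That is about 3 control deaths (0.0275·118.5 = 3.3), against 41 planned (0.35·118.5 = 41.5).
- A 33% relative reduction applied to the low control rate: CP is 13.2% at p = 5% and 9.7% at p = 4%, so about 4%.
- No further effect: Z(p) = 1.490 at p = 10.4%.

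**4. The override example, as section 7.7 literally words conditional power** (the chance of finally observing a 33% reduction). Take p = 35% and a 50% reduction at half-way: 41.5 deaths against 20.7. If both arms then run at 35%, the expected totals are 82.95 and 62.2. The final reduction reaches 33% when T − (2/3)C ≤ 0, where T and C are total deaths on combination and control. The mean of that quantity is 62.2 − 55.3 = 6.9. Its SD, from the second half only, is √[118.5·0.35·0.65·(1 + 4/9)] = 6.2. The probability is Φ(−1.11), about 13%. Under the current trend the mean is 41.5 − 55.3 = −13.8 and the SD 5.4, giving about 99%. Across control mortality of 5% to 35% and every convention tried, the chance ran from about 12–13% to 99%. It never fell below 10%.

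**5. Exposure.** If the meeting is held and enrolment continues, at most 474 − 237 = 237 evaluable patients follow. The true figure is lower, because some will already have been randomised while 6-week outcomes are awaited.

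**The case against.** The strongest reply has four parts.

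*The rule is narrower than it may look.* A reader might infer that the investigators alone decide on the observed effect. They are three of seven listed members, the effect is one of three considerations, and the meeting is held only when the threshold is crossed. If the planned effect is true, that happens in 0.6% to 11% of trials under the first two conventions. This stands, but it does not remove the disclosure when the meeting is held.

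*The route to bias is limited.* Allocation is concealed with varying block lengths, so a shift in enrolment affects both arms. Treatment duration and added antifungals are open to influence in any open-label trial. This stands as a limit on size. Knowing the interim effect is still a further source of influence that the design need not create.

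*Outside bodies have oversight.* A reader might infer that nobody else could act on excess deaths. The documents do not support that. Section 8.1 provides for suspension pending ethics review if the disadvantages prove significantly greater than foreseen, and section 8.6 requires an annual safety report that weighs efficacy against harm. What can be said is that no other between-arm mortality review by a named body is specified.

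*Access may be settled elsewhere.* An unseen analysis plan or charter may restrict it. Section 9.6 does not say that the coordinating investigator runs the interim, and section 12.1 sends coded data to a statistician. So it cannot be inferred that this investigator prepares the interim result. But section 7.7 itself gives the observed effect to the principal investigators, and another document could not withhold it without contradicting the protocol.

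**Conclusion.** The point holds as a weakness in how the interim decision is governed. Section 7.7 lets principal investigators weigh the observed between-arm effect, with no DSMB and no stated restriction, and up to 237 of 474 evaluable patients could follow with those investigators informed.

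A reader might infer that the final test is compromised. It is not: the look is for futility only, and continuing past a futility signal leaves the type I error at or below 0.05. The harm is operational bias and loss of credibility.

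The override example is unrealistic rather than strictly impossible. For significance it needs control mortality below about 2.8%, 4% or 10%, depending on the convention, against 35% planned. On the literal wording it did not arise at control mortality of 5% to 35%. It therefore gives no practical reason for investigators to see the arm-level effect, and it leaves the override as discretion without guidance.

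The figures assume a normal approximation, a final critical value of 1.96 and equal arms at half-way. The protocol names the three hospitals as the principal investigators' centres. That they also recruit is a natural reading, but it is not stated in so many words.

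**What to change.** Amend section 7.7 so that:

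- (a) the existing study statistician runs the interim, and arm-level results go only to listed team members who neither recruit nor treat. By their titles these would be the statistician, the funder delegates and the patient representative;
- (b) the investigators supply recruitment figures and pooled mortality, and receive only continue or stop;
- (c) the low-event override is based on pooled mortality, and the effect assumed for the remaining patients in conditional power is stated.

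The same closed session can also look at mortality in the direction of harm.

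The cost is protocol wording and a short closed-session procedure, with no new committee and no extra patients. There are downsides. The investigators lose their vote on arm-level data. A message that the threshold was crossed, or that the trial continues, still reveals something approximate. The closed group is not fully independent, since funders have an interest, and it may lack a clinician for the harm review. A newly appointed independent statistician would be stronger, but is an added resource that this fix does not require.
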